## 6.5. Visit Windowing

The CSP defines for each of the study visits from Visit 3 (Week 4, Day 28) to EOS (Visit 12, Week 56, Day 392), a  $\pm$ 7-day visit window. However, the visit schedule may not be followed due to various reasons such as patients travel arrangements, etc. The goal is to use all available data such as data from unscheduled visits to minimize missing data at scheduled, nominal visits. Therefore, programmatic visit windowing will be applied to analysis datasets preparation.

Based on the actual visit date, the actual measure will be allocated to the specific visit using visit intervals as specified in Table 4. After all observations have been evaluated following the defined visit intervals, it may appear that an interval has multiple (valid) observations for the same assessment within the same scheduled, nominal visit. For the analysis, one of these observations will be used while the selection will follow the below rules (in the sequential order given):

- Select the observation closest to the target Study Day,
- Select the latter observation if 2 observations are equally close to the target Study Day.

CONFIDENTIAL Page 36 of 139

Table 4:	Visit	Wind	owing
----------	-------	------	-------

Scheduled Visit (Nominal Visit)	Scheduled Visit Day (Study Day)	Visit Intervals
Screening		<= -1
Day 1	1	1
Week 4	28	2 to 49*
Week 10	70	50 to 91
Week 16	112	92 to 133
Week 22	154	134 to 175
Week 28	196	176 to 217
Week 34	238	218 to 259
Week 40	280	260 to 301
Week 46	322	302 to 343
Week 52	364	344 to 378
Week 56	392	>=379

\*Note: Visit windowing will not be applied to assessments completed every day, or every 2 weeks. Refer to PRO assessments as described in Section 6.7.5. Further, in cases where the first IP was administered after day of randomization, visit windowing will not overrule assignment of baseline record and windowing will not be applied. As an example, consider a participant with date of randomization at 22-Jul but IP administration was at 24-Jul. Data reported at date of IP administration would have analysis date equal to 3 (date – date of randomization + 1). If visit windowing applied, participants would not have a baseline. Therefore, visit windowing will not be applied for those records who fulfill the constraint of the baseline.

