#### 6.3.1.2. Subjects Already Enrolled in the Study

If the decision is to continue the participation of subjects already enrolled, the following steps should be taken:

- If a subject is not able to complete a protocol-specified study visit, it may be necessary to adjust the visit schedule, convert in-clinic visits to telemedicine visits, and/or postpone study procedures until the next available in-clinic study visit. If there is information available from previous visits (ie, laboratory assessments) that requires follow-up procedures or other safety assessments, the Investigator will decide if an on-site visit or home healthcare visit is required or whether the subject's safety can be preserved by other means
- If study participants no longer have access to investigational product, specific procedures should be put in place to ensure delivery of investigational product to subject provided all safety considerations and applicable health authority requirements have been addressed.

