#### 3. STUDY DESIGN

## 3.1. Summary of Study Design

This is a Phase 3, randomized, double-blind, placebo-controlled, parallel-group, multicenter, multinational study to assess the efficacy, safety, and tolerability of 2 doses of brensocatib compared with placebo in participants with NCFBE. Approximately 1,620 adult participants will be randomized in a 1:1:1 ratio to 3 treatment arms (540 participants per treatment arm) to receive brensocatib 10 mg QD, brensocatib 25 mg QD, or matching placebo QD for 52 weeks (refer to Section 3.3). For this study, the adolescent population is defined as participants ≥12 to <18 years of age who have had at least 1 PE in the prior year. Approximately 40 adolescent participants will be randomly assigned in a 2:2:1 ratio to receive brensocatib 10 mg QD, brensocatib 25 mg QD, or matching placebo QD for 52 weeks.

After baseline, participants will return to the study site for in-clinic visits at Weeks 4, 16, 28, 40, 52 (end of treatment [EOT]), and 56 (end of study [EOS]), during which they will be assessed for PEs and undergo clinical laboratory tests, vital signs measurement, and assessment by means of questionnaires (BEST, QoL-B, PGI-S/PGI-C, QoL-PCD, and EQ-5D-5L). In addition, collection of the days of work and/or school missed due to PE will occur. Telephone visits will occur at Weeks 10, 22, 34, and 46, during which collection of AEs, concomitant medications, smoking status, periodontal complaints, questionnaires (as mentioned above), and assessment for occurrence of PEs will occur. At Visit 11 (Week 52/EOT) participants will discontinue all study treatment and will be followed for a 1-month follow-up period, during which initiation of any new medical or non-medical therapy for NCFBE should be avoided.

At Visit 12 (Week 56/EOS), participants will complete all protocol-specified assessments and EOS procedures.

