#### 6.1. General

All summaries will be provided by treatment group, if not stated otherwise (see Section 6.4.2 below). Some presentations will describe specific populations, and this will be evident in each output as necessary.

Descriptive statistics for continuous variables will be calculated at scheduled visits (nominal time points for PK concentration) and will include the number of participants in the treatment group/dose level of the respective Analysis Set (N in column header of the table), the number of non-missing observations (n), arithmetic mean, standard deviation (SD), CV%, median, minimum, and maximum. For NSP concentrations and percent change from baseline in blood and sputum, mean, SD, CV%, median, minimum, maximum will be determined. For brensocatib plasma concentrations and PD results, the geometric mean (GM) with 95% CI and geometric coefficient of variation -percentage (gCV)%, and the number of observations below limit of quantification (BLQ) will also be reported. The GM will be derived by calculating the arithmetic mean of the log-transformed observations and then back-transforming the mean by exponentiation. The gCV% will be calculated as: 100\*sqrt (exp [variance of the log-transformed values] - 1). GM -and gCV% will only be calculated for quantifiable values above 0 (if at least 1 value are less than 0, e.g., for PD parameters, no GM and gCV% will be displayed but left empty). Listings will present the data in its original format.

Categorical variables will be summarized by counts and by percentage of participants in the corresponding categories. The number of participants in the treatment group/dose level of the respective Analysis Set (N in column header of the table) and the number and percentage of non-missing observations in each category will be provided. A category including missing assessments may be added if appropriate. Footnotes will specify the denominator used for the percentages.

In case of mis-randomization to incorrect strata, participants will be analyzed according to the strata into which they were randomized.

Data from unscheduled visits will not be used in summaries, except for the derivation of baseline (see Section 6.4.3).

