### 6.4.9. Data Re-allocation for Early Discontinued Participants

Data collected at multiple visits (spirometry, smoking status, vital signs, and laboratory data) recorded at the EOT visit (Week 52, Visit 11) for early discontinued participants will be reallocated. Re-allocation will depend on the actual date of the EOT visit and the closest expected (scheduled) visit date.

For example, if the last visit performed before the EOT visit is Visit 4, the data recorded at the EOT visit will be re-allocated to Visit 5 or 6 depending on the date of the study termination visit. If the study termination visit was performed less than 7 days after the preceding visit, e.g., if the EOT visit was performed in the same visit window as defined in Section 6.5, data other than PEs/AEs/SAEs/AESIs recorded at the EOT visit will not be re-allocated and they will be excluded from the statistical analysis, summary tables and figures. For each assessment, only the visits at which the assessment was scheduled per CSP will be considered for re-allocation. This means that vital signs and laboratory data can be re-allocated to Visits 3, 5, 7 and 9 only. Visit windowing as defined in Section 6.5 will be considered for allocation of data.

Assessments completed every 2nd week, e.g., PGI-S, PGI-C, and QoL-B, will not be reallocated.

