#### 8.3.3.1. Main Analyses

The Main Estimand of the change from baseline in post-bronchodilator FEV1 (L) at Week 52 is the On-Study Estimand in which all observed data will be included in the analysis (see Section 2). The ITT Analysis Set (see Section 5.2) will be used for this Estimand. The derivation of the endpoint is detailed in Section 6.7.3. Tabulations described below will not be limited to Week 52 but summarize all scheduled time points.

Pre- and post-bronchodilator FEV1 assessments at baseline and Weeks 16, 28, 40, 52 will be summarized by treatment group using descriptive statistics. The summary will include changes from baseline, too.

Change from baseline in post-bronchodilator FEV1 (L) will be analyzed using a linear repeated measures model including treatment group, visit, treatment-by-visit interaction, sputum sample being classified as positive or negative for *Pseudomonas aeruginosa* at Screening Visit, the number of prior PEs [<3 or  $\ge$ 3] in the previous 12 months, stratification region (North America, Europe, Japan, and the Rest of the World), and age group (adult, adolescent) as fixed effects, and baseline value as covariate. The variance-covariance structure will be compound symmetric with the robust sandwich variance estimator (option EMPIRICAL in the PROC-Statement). This analysis will be performed in SAS using MIXED procedure. The OM option will be used to adjust the coefficients for the LSMEANS to reflect the observed data.

If the age group covariate creates estimability issues, it may be removed. If the model still does not converge after removing the age group covariate, other handling including using the parametric covariance estimator instead of the robust sandwich covariance estimator may be applied. When using the parametric covariance estimator, the restricted maximum likelihood (REML) estimator will be applied, with the variance-covariance structure being applied with the following sequence: UN -> TOEPH -> ARH(1) -> CSH. If the model still does not converge, the maximum likelihood estimator will be applied instead of the REML estimator, with the same sequence of the possible variance-covariance structures. The adjustment will be added to the footnote of the corresponding outputs.

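### SAP Table 4 windows are built on all visits, including phone visits and Week 56, so off-schedule FEV1 values can fall at visits the FEV1 model does not contain

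*SAP*

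**What the plan says.** SAP 6.5 sets the rule: "Based on the actual visit date, the actual measure will be allocated to the specific visit using visit intervals as specified in Table 4". Its purpose is also stated: "The goal is to use all available data such as data from unscheduled visits to minimize missing data at scheduled, nominal visits". The exemptions are narrow: "Visit windowing will not be applied to assessments completed every day, or every 2 weeks", and records that qualify as baseline are left alone. Spirometry is not exempt.

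Table 4 has a row for every post-baseline visit. Four of these are by telephone: "Telephone visits will occur at Weeks 10, 22, 34, and 46". The last row, Week 56, takes everything from Day 379.

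Protocol 7.3 and Protocol Table 5 schedule post-baseline spirometry only at Weeks 16, 28, 40 and 52. SAP 8.3.3.1 follows this ("assessments at baseline and Weeks 16, 28, 40, 52 will be summarized by treatment group") and says the main FEV1 analysis takes in every observed value. In SAP Appendix I the visit identifier for the FEV1 model has four levels, Weeks 16, 28, 40 and 52.

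Two other SAP rules bear on the point. SAP 6.4.9 re-allocates end-of-treatment (EOT) data of early-discontinued participants, names spirometry among the data covered, and admits only visits at which the assessment is scheduled. SAP 6.1 says: "Data from unscheduled visits will not be used in summaries, except for the derivation of baseline".

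**The concern.** A window table should place an off-schedule measurement at the nearest visit where that measurement is analysed. Table 4 does this for data collected at every visit. For spirometry, the rows for Weeks 22, 34 and 46 lie between modelled visits, and the Week 56 row follows directly after Week 52. An FEV1 value landing in one of these rows has no place in the model, and nothing in 6.5 sends it back to a modelled visit.

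Post-bronchodilator FEV1 at Week 52 is Family 4 in the multiplicity procedure (SAP 6.3.1). Under Appendix I, a participant with no value at a modelled visit gets a record with a missing response. In the tipping-point analysis, if it is run, that value would be imputed and could be penalised although it had been measured. The people affected are those with delayed or advanced visits, which 6.5 itself expects.

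**Working it through.** **Inputs.** Scheduled days and intervals: SAP Table 4. Spirometry schedule: Protocol 7.3. Visit tolerance of ±7 days: Protocol Table 5. Modelled visits: SAP Appendix I.

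**Step 1: reproduce Table 4.** Upper limit = midpoint of consecutive scheduled days, over all visits.

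- (28+70)/2 = 49; (70+112)/2 = 91; (112+154)/2 = 133
- (154+196)/2 = 175; (196+238)/2 = 217; (238+280)/2 = 259
- (280+322)/2 = 301; (322+364)/2 = 343; (364+392)/2 = 378

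All nine match the table, so telephone visits and Week 56 shape the boundaries for every assessment.

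**Step 2: how far an FEV1 value can move and stay in its row.** Shift = interval limit minus target day.

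| Visit | Target | Interval | Earliest shift | Latest shift | Next row, early / late |
|---|---|---|---|---|---|
| Week 16 | 112 | 92 to 133 | -20 | +21 | Week 10 / Week 22 |
| Week 28 | 196 | 176 to 217 | -20 | +21 | Week 22 / Week 34 |
| Week 40 | 280 | 260 to 301 | -20 | +21 | Week 34 / Week 46 |
| Week 52 | 364 | 344 to 378 | -20 | +14 | Week 46 / Week 56 |

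A value therefore leaves its row at 21 or more days early, at 22 or more days late (Weeks 16, 28, 40), or at 15 or more days late (Week 52). Each adjoining row is outside the model. The late side is tightest at the endpoint visit: the protocol window for Week 52 ends at 364+7 = Day 371, and Day 379 is 8 days past it.

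**Step 3: very large shifts.** These can reach a neighbouring modelled visit. A Week 28 test 64 days late falls on 196+64 = Day 260, which is Week 40. A Week 52 test 63 days early falls on 364-63 = Day 301, also Week 40.

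**Step 4: calendar share.** From Day 92 to Day 378 there are 378-92+1 = 287 days. Weeks 22, 34 and 46 take 42 days each, so 126/287 = 43.9% of days map to an unmodelled row. This describes the table, not the data.

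**Step 5: spirometry-only midpoints.** (112+196)/2 = 154; (196+280)/2 = 238; (280+364)/2 = 322. With these, Days 134 to 175, 218 to 259 and 302 to 343 all map to a modelled visit; Day 343, for example, goes to Week 52 instead of Week 46.

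**The case against.** The strongest reply is that little is at risk. Table 4 tolerates about three times the protocol's ±7 days on most sides, so only markedly off-schedule tests are touched. That stands, and no document says how many there are.

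Four stronger readings are tempting and are not supported:

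- *Much early-discontinuation spirometry is lost.* A reader might infer this by applying Table 4 to EOT dates. SAP 6.4.9 already limits such data to visits where the assessment is scheduled, which excludes telephone visits for spirometry. What remains is a question of precedence, because 6.4.9 also refers back to the 6.5 windows. For an EOT test on Day 150, the nearest scheduled spirometry visit is Week 16 (38 days away, against 46 for Week 28), while Table 4 says Week 22.
- *The 6.4.9 example is wrong.* It reads "the data recorded at the EOT visit will be re-allocated to Visit 5 or 6 depending on the date of the study termination visit", and Visit 6 is a telephone visit. But 6.4.9 also covers smoking status, which Protocol Table 5 collects at telephone visits, so Visit 6 is a valid target for that item.
- *About 44% of FEV1 data are affected.* The figure is a share of calendar days. Visits cluster around their target days.
- *SAP 6.1 and 6.5 flatly contradict each other.* SAP 6.1 speaks of summaries and 6.5 of preparing analysis datasets. SAP 6.7.3 separately excludes optional pulmonary function tests from all analyses. A clarifying sentence is needed, no more.

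The protocol's public-health provision is also weaker evidence than it looks. It allows sites to "postpone study procedures until the next available in-clinic study visit". After Weeks 16, 28 and 40, that next visit is itself a modelled one, so the skipped visit would be empty under any windowing. Only for Week 52 is the next in-clinic visit Week 56 (Day 392 ±7, Days 385 to 399), entirely inside the Week 56 row.

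**Conclusion.** The defect is real but narrow. Followed as written, SAP 6.5 generally removes measured FEV1 values from the model once they pass the limits in Step 2, against the section's stated goal and the inclusion rule of 8.3.3.1. It mainly concerns off-schedule spirometry other than early-discontinuation EOT tests. The most important case is a Week 52 test on Day 379 or later.

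The effect on the treatment estimate cannot be computed from the documents. For scale only, each 1% of Week 52 tests outside Days 344 to 378 would be about 5 participants per arm (0.01 × 540 = 5.4); the rate itself is unknown.

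The conclusion assumes that 6.5 is programmed literally and that no separate specification already restricts spirometry to its scheduled visits. The change should be made before database lock because it is cheap and the endpoint is formally tested.

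**What to change.** - Extend the 6.4.9 restriction to 6.5: allocate each assessment only to visits at which it is scheduled. This also covers EQ-5D-5L, which SAP 6.7.5.6 sends to the same windows.
- For spirometry, put boundaries at the midpoints: Week 28 = Days 155 to 238, Week 40 = Days 239 to 322, Week 52 from Day 323. Keep the existing rule that the value closest to the target day is used.
- State the outer limits. Week 16 should not start at Day 2, which would count a test days after randomization as a Week 16 response; keeping Day 92 is one option. Week 52 needs an explicit last day.
- State in 6.4.9 that EOT spirometry goes only to scheduled spirometry visits and that this takes precedence over Table 4.
- State that 6.5 governs unscheduled data in windowed analyses, subject to the 6.7.3 exclusion of optional tests.

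There is a precedent: SAP Table 6 already gives QoL-B, PGI-S and PGI-C their own windows. The cost is SAP wording and programming. The downside is that a few values lie further from the nominal day, up to 154-112 = 42 days late at Week 16 or 364-323 = 41 days early at Week 52. A sensitivity run with the current Table 4 windows covers this.

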## 6.6. Reporting of Data After Early Discontinuation of IP

All participants who discontinued IP early are encouraged to stay in the study for continued assessments following the same study procedures until the EOS. Reasons for early IP discontinuation will be recorded. If a participant withdraws consent from continued monitoring, the EOS visit will be completed.

The purposes for collecting these data are to permit full efficacy data ascertainment per the ITT principle in accordance with the On-Study estimand and to allow continual monitoring of participant safety for the 4-week follow-up period after IP discontinuation.

Reporting rules for data collected after early discontinuation of IP are outlined for each data type (efficacy, safety, pharmacokinetic, pharmacodynamic, etc.) per the corresponding estimand, specifically the ICE handling strategy.

Safety data that are excluded from treatment emergent period, i.e., data collected after the 4-week follow-up post early discontinuation of IP, will be reported separately and will include basic summaries of:

- AE, SAEs and AESIs, (non-treatment emergent)
- Laboratory
- Concomitant medication.

Other collected safety data will be listed.

CONFIDENTIAL Page 37 of 139

### 6.7. Definitions and Derivations of Efficacy Variables

### 6.7.1. Pulmonary Exacerbations

Only exacerbation events that meet the protocol definition of PE diagnosis confirmed by an independent adjudication committee will be included into the analysis (refer to Section 10.4.6.1.1 of the CSP for further details and the Clinical Endpoint Committee [CEC] Charter).

The calculation of the time at risk as well the inclusion of data into the analysis depends on the underlying Estimand. Refer to Table 5 for further details. In general, participants' time at risk will be the time on study excluding the time during exacerbations.

Table 5: PEs to be included into the analysis and time at risk based on Estimand

Estimand	PEs included in	
Name	the analysis	Time at risk
On-Study	All observed PEs	Date of Week 52 visit / early study
(Primary)	up to Week 52 who	discontinuation  – date of randomization + 1 minus
	meet the protocol	the sum of number of days the participant
	defined criteria of	experiences exacerbation events that meet the
	PE diagnosis	protocol definition of PE diagnosis (end date of the
		PE – start date of the $PE$ + 1). Refer to
		Section 6.7.1.1 for further instructions in case of
		combined PEs.
On-Treatment	All observed PEs	Date of last IP intake / date of first ICE onset –
and On-IP	up to end of IP /	date of first IP intake + 1 minus the sum of number
(Supplementary)	first ICE onset who	of days the participant experiences exacerbation
	meet the protocol	events that meet the protocol definition of PE
	defined criteria of	diagnosis prior to the first ICE (end date of the PE
	PE diagnosis	– start date of the PE + 1). Refer to Section 6.7.1.1
		for further instructions in case of combined PEs.

Rules defined above will not be applied to the analysis of PEs as AEs, e.g., not fulfilling protocol-defined criteria (see Section 7.1 of the CSP).

If a PE is ongoing at EOS, the PE end date will be EOS date, given query for resolution failed. If the PE end date is longer / after the EOS date, then the PE end date will be set to the

CONFIDENTIAL Page 38 of 139

-

<sup>2 Note: The Week 52 visit is the EOT visit per CSP and the date is determined through the eCRF form "V11 (EOT or E/D)". The date of last IP administration will be determined through eCRF form "End of Treatment" as indicated in Section 6.4.2. Participants who complete IP and the Week 52 visit as per protocol the on-study and on-treatment estimand will select the same data for analysis. Participants who discontinue from IP early, the date of Week 52 visit will be calculated as MINIMUM(date of EOS, date of randomization + 363) to match the scheduled date of Week 52 to keep similarity across participants discontinuing the study early.

EOS date to calculate the time at risk. Participants ongoing at time of primary analysis, e.g., adolescents, the date of cut-off will be used as PE end date.

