## 10.4.6.1.4. Supportive Analyses for Primary Endpoint

The supportive estimand for the primary endpoint is the On-Treatment estimand and will utilize the ITT Analysis Set. The same negative binomial regression model will be implemented for this estimand; however, only data up until the occurrence of a relevant ICE (ie, early discontinuation of randomized study treatment, early discontinuation of standard of care, or addition of chronic antibiotics) will be included in the analysis. Time at risk will be defined as the time of exposure until the occurrence of an ICE or until the last dosing date of IP if no ICE occurred. Time during an exacerbation will be excluded from the time at risk.

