## 2.1. Primary Objective and Estimands

The primary objective is to evaluate the effect of brensocatib at 10 mg and 25 mg compared with placebo on the adjudicated Annualized Rate of PEs.

The primary and supplementary Estimands for the primary objective including their attributes (i.e., the variable, the population level summary, the treatment regimen, and the strategies per the ICH E9(R1) Addendum to be implemented for addressing the study's relevant ICEs) are presented in the Table 1 below. The population attribute for these Estimands is participants with NCFBE.

Table 1: Primary Endpoint and Estimands

Variable	Population Level Summary	Estimand Name	Treatment Regimen	ICEs/Strategy	Section
Annualized Rate of PEs	Rate Ratio	Primary: On- Study	Assignment to IP regardless of discontinuation or modifications to standard of care	Early discontinuation from randomized IP/ Treatment Policy Modification to standard of care/ Treatment Policy	8.2.1
		Supplementary: On-Treatment	Standard of care + randomized IP	Early discontinuation from randomized IP/ While On-Treatment Modification to standard of care/ While On-Treatment	8.2.5
		Supplementary: On-IP	Randomized IP regardless of modifications to standard of care	Early discontinuation from randomized IP/ While On-Treatment Modification to standard of care/ Treatment Policy	8.2.5

CONFIDENTIAL Page 14 of 139

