#### **6.2.1.** Identification of ICEs

The following subsections will describe the two ICEs defined for this study.

If both ICEs occur at the same date, e.g., early discontinuation from randomized IP and modification from standard of care at the same date, the early discontinuation from randomized IP will be prioritized. Within standard of care the discontinuation from standard of care will be prioritized over addition of new chronic antibiotics.

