#### 6.2.1.1. Early Discontinuations from Randomized IP

Early discontinuation from randomized IP will be identified through the eCRF "End of treatment". A participant will be considered as early discontinued from randomized IP if the question "Did the subject complete the planned treatment per protocol?" was answered with "No".

The date entered for "Last dose date" will be used as date of ICE onset.

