#### 6.2.2. Time to (first) ICE

Time to first ICE in days will be calculated as

Time to (first) ICE (days) = start date of first ICE - date of reference + 1.

Participants who do not have an ICE during the 52-Week treatment period will be censored at time of EOT.

The date of reference will be the date of first IP administration, if not stated otherwise. If a participant was randomized but not treated with IP, the participant will be censored at study day 1 (day of randomization).

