#### 8.3.1.3. Supplementary Analyses

The supplementary Estimand for the time to first PE over the 52-Week treatment period is the On-IP Estimand (see Section 2) and will utilize the ITT Analysis Set (see Section 5.2). The time-to-event model of the main analysis will be implemented for this Estimand (see Section 8.3.1.1). Participants who do not have an event during the 52-Week treatment period will be censored at the day of last treatment administration.

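### SAP Table 5 gives On-IP and On-Treatment one cut-off at the first intercurrent event, which, read literally, ends On-IP follow-up at an antibiotic change and contradicts the On-IP definition

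*SAP*

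**What the plan says.** SAP Table 1 lists two supplementary estimands for the annualized PE rate. On-Treatment handles both IP discontinuation and modification of standard of care by a while-on-treatment strategy. On-IP handles IP discontinuation that way but handles modification of standard of care by treatment policy; its regimen is "Randomized IP regardless of modifications to standard of care". SAP Section 2 describes On-IP in the same sense, and Table 2 repeats it for severe PEs.

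Table 5 in SAP 6.7.1 turns the estimands into event counts and time at risk. On-Treatment and On-IP share one row. PEs count up to the end of IP or the first ICE onset, time at risk ends at "Date of last IP intake / date of first ICE onset", and the exacerbation days subtracted are those meeting the protocol "diagnosis prior to the first ICE (end date of the PE" minus its start date, plus 1).

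SAP 6.2.1 states: "The following subsections will describe the two ICEs defined for this study". They are early discontinuation of IP (6.2.1.1) and modification of standard of care, meaning chronic antibiotics (6.2.1.2). SAP 6.2.2 computes "Time to (first) ICE (days) = start date of first ICE - date of reference + 1", without limiting the ICE by type or estimand.

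For time to first PE the SAP is more specific. Section 6.7.1.6 attaches the rule of last IP intake or first ICE onset to On-Treatment only. Section 8.3.1.3 says that On-IP participants without an event "will be censored at the day of last treatment administration".

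**The concern.** The handling of antibiotic changes is the only difference in ICE strategy between On-IP and On-Treatment. A shared cut-off at an unqualified first ICE removes that difference at the derivation stage, whatever Tables 1 and 2 say. A programmer who follows Table 5 as written would produce two supplementary analyses of the primary endpoint from the same counts and the same offsets, with the one labelled On-IP not estimating what On-IP is defined to estimate. For severe PEs, On-IP is the only supplementary estimand, so on-drug severe events after an antibiotic change would drop out of it.

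**Working it through.** No stated figure underlies this point, so the check is a comparison of sections, then a worked example and an illustrative size.

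**1. Is Table 5 the operative rule?** SAP 6.7.1.2 sends both the number of PEs and the time at risk to Table 5. SAP 6.7.4 applies the same derivation to severe PEs. SAP 8.2.5 and 8.3.4.3 name the model and the analysis set for the supplementary estimands but give no other On-IP cut-off. Nothing overrides Table 5 for these two rates.

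**2. Can the shared row be read so that the two estimands stay apart?**

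- *ICE means IP discontinuation only.* SAP 6.2.1.1 says that the last dose date "will be used as date of ICE onset" for that event, so the first-ICE clause would add nothing to last IP intake. On-Treatment would lose its antibiotic rule. The two derivations would still coincide, with On-Treatment now the wrong one.
- *The slash means respectively.* The row names On-Treatment first, so On-Treatment would end at last IP intake and On-IP at the first ICE. That is the reverse of Table 1.
- *ICE means any event handled while-on-treatment under the estimand in question.* This works, but the SAP does not say it.

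**3. Comparison with the protocol.** Protocol 10.4.6.1.4 describes On-Treatment only. It refers to a relevant ICE, lists the types, and defines time at risk as exposure "until the occurrence of an ICE or until the last dosing date of IP if no ICE occurred". Table 5 has the same substance in different words, without the list, and extends it to On-IP.

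**4. Worked example (all values assumed).** A participant takes IP on days 1 to 364, starts a new chronic antibiotic on day 100, and has 10-day PEs starting on days 60 and 200. Time at risk = end day − first IP day + 1 − PE days in the period; rate = PEs ÷ time at risk × 365.25.

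| Derivation | End day | PEs | Time at risk (days) | Rate per year |
|---|---|---|---|---|
| On-Treatment, Table 5 | 100 | 1 | 100 − 1 + 1 − 10 = 90 | 1 ÷ 90 × 365.25 = 4.06 |
| On-IP, Table 5 read literally | 100 | 1 | 100 − 1 + 1 − 10 = 90 | 4.06 |
| On-IP, as Table 1 defines it | 364 | 2 | 364 − 1 + 1 − 20 = 344 | 2 ÷ 344 × 365.25 = 2.12 |

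The first two rows are the same for any participant, because the rule is the same. The example shows that the derivations differ; it says nothing about the direction of any effect on the rate ratio.

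**5. Illustrative size.** The documents give no share of participants with an antibiotic ICE. Assume that a share q has one halfway through a full 52 weeks on IP, or at a uniformly distributed time, which loses half on average. The on-IP follow-up dropped is then q × 0.5.

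- q = 5%: 0.05 × 0.5 = 2.5%
- q = 10%: 0.10 × 0.5 = 5%
- Wider range, q = 2% to 20%: 1% to 10%

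**The case against.** The strongest reply is that Table 5 should be read with its surroundings. SAP 6.7.1 introduces it by saying that time at risk depends on the estimand, SAP 6.6 ties the reporting of data after IP discontinuation to each estimand's ICE strategy, and Table 1 gives that strategy. On that reading the first ICE under On-IP can only be IP discontinuation, and the shared row serves both estimands. A blinded data review before lock (SAP 6.2) also gives a chance to settle the matter.

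This reading is sensible and probably intended, so it would go too far to say that the SAP fixes On-IP and On-Treatment as one analysis. They coincide under the literal rule. But the reader has to supply a restriction that Table 5 omits and that 6.2.1 and 6.2.2 do not provide, and where the SAP wanted the two apart, for time to first PE, it wrote separate rules.

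The reply is also right that the ICE is narrow. SAP Section 2 counts a new antibiotic only if taken for more than 28 days and not for a concurrent PE. SAP 6.2.1.2 does not count a dose or frequency change of the same antibiotic within 7 days as discontinuation, and excludes standard of care stopped on the same date as IP. The true share could be well below 5%. The roughly 20% on chronic antibiotics (SAP Section 2) is a baseline prevalence, not a rate of change.

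**Conclusion.** The contradiction stands and should be corrected, but its reach is limited. As written, Table 5 gives On-IP the On-Treatment cut-off for the PE rate and the severe-PE rate, against SAP Section 2 and Tables 1 and 2 and out of line with 8.3.1.3. Both affected analyses are supplementary. The primary On-Study analysis, the multiplicity procedure and the power do not depend on this row.

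The 2.5% to 5% loss rests wholly on the assumed 5% to 10% changing at mid-study. The effect on the rate ratio cannot be derived.

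Two further inferences are tempting but unsupported:

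- *That the SAP can no longer separate stopping drug from changing antibiotics.* Time to first PE has its own On-IP rule, the FEV1 and QoL-B On-IP analyses do not use Table 5, and SAP 8.4 tabulates each ICE type by arm. For severe PEs a tipping-point analysis (8.3.4.2) also remains.
- *That the lost follow-up falls mainly on participants who are exacerbating.* This is plausible, but no figure in either document supports it.

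**What to change.** Split the shared row of SAP Table 5 in two.

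- **On-IP:** count PEs and time at risk from first to last IP intake, regardless of antibiotic modification, and subtract all PE days in that period.
- **On-Treatment:** count PEs and time at risk from first IP intake to the earlier of last IP intake and first ICE onset of either type, and subtract PE days before that cut-off.

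The cost is one extra table row and a separate end date in the derivation of the two rates. It needs no new data and should be made before unblinding.
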